5.2. Number of Participants

The number of healthy male participants and the required number of evaluable participants are outlined in Table 1.

Part	Participants per cohort	Evaluable participant number per cohort	Evaluable participant definition
A (Cohorts 1-2)	9 (6:3 GSK3358699 : Placebo)	6	Complete both screening and all their planned treatment Periods.
B (Cohort 3)	6 (all receive GSK3358699)	5	Complete both screening and both treatment Periods.
C (Cohort 4)	14 (10:4 GSK3358699 : Placebo)	9	Complete both screening and the 14 day treatment Period and subsequent 48 h assessment Period.
C (Cohorts 5-7)	18 (9:9 GSK3358699 : Placebo)	12	Complete both screening and the 14 day treatment Period and subsequent 48 h assessment Period
C (Cohort 8)	20 (10:10 GSK3358699 : Placebo)	14	Complete both screening and the 14 day treatment Period and subsequent 48 h assessment Period.

Table 1 Number of Participants

2017N332348_05

CONFIDENTIAL

Participants who are randomized into a particular part of the study can be enrolled in another part of the study, as well as be enrolled in a later cohort of the same part of the study in Part C, if they still fulfil all eligibility criteria (which means that participants having received LPS challenge in Part A will not be eligible to participate in another part of the study).

Additional participants/cohorts may be enrolled in Part A or Part C to allow for evaluation of additional dose levels or alternative regimens, including for challenges, as detailed in Section 7.2. No more than 9 additional participants will be included as part of a new cohort in Part A and no more than 20 additional participants will be allowed as part of a new cohort in Part C (ie in addition to Cohort 4-8 participants).

If participants prematurely discontinue the study during Part A, additional replacement participants may be recruited and assigned to the same treatment sequence, starting from the next planned dosing Period following the premature discontinuation, at the discretion of the Sponsor in consultation with the investigator.

If a participant chooses to participate in, or is eligible for, the dose escalation treatment Periods only in Part A as described in Section 5.1.1.1, a new participant will be recruited for the challenge treatment period (treatment Period 4) only and will be regarded as a replacement subject, assigned to the same treatment sequence. This will occur at the discretion of the Sponsor in consultation with the investigator.

If participants prematurely discontinue the study during Part B, additional replacement participants may be recruited and assigned to the same treatment sequence, starting from the beginning of the first treatment Period, at the discretion of the Sponsor in consultation with the investigator.

If participants prematurely discontinue the study during Part C, additional replacement participants may be recruited and assigned to the same treatment sequence, starting at the beginning of the treatment Period, at the discretion of the Sponsor in consultation with the investigator.

5.3. Participant and Study Completion

A participant is considered to have completed the study if he has completed all study visits, including the follow up visits, for which he was eligible or to which he consented.

The end of the study is defined as the date of the last visit of the last participant in the study.

5.4. Scientific Rationale for Study Design

This study will be the first administration of GSK3358699 in human participants. The primary purpose of the current study is to characterise the safety and tolerability of GSK3358699 in healthy male participants within a pre-defined and controlled PK and PD range. The study will additionally seek to understand the secondary and exploratory endpoints highlighted in Section 4. Specific scientific considerations which contribute to the study design include:

- In Part A, this study employs an interlocking crossover design to allow more accurate extrapolation of PK and PD data within participants at different dose levels. In addition, this design minimises participant numbers across the single ascending dose (SAD) part of the study and allows for a minimum 28 day washout Period between doses for a particular cohort. To maximise the safety, PK and PD 'within-participant' information gathered during the dose escalation period, which will adequately inform dosing in treatment Period 4 and in Parts B and C of the study, the flexibility of participation in Part A has been enhanced to facilitate subject recruitment and retention.
- In Part B, the effect of food will be investigated. An early understanding of any effect of food on exposure or PD will improve dose selection in future clinical studies with GSK3358699. Data from Part B is not intended to inform the conduct of Part C of the present study.
- In Part C, it is planned that five repeat dose cohorts will be administered multiple doses of GSK3358699 or placebo. As part of this, investigations into the dose response will be made.
- According to a Physiologically Based Pharmacokinetic (PBPK) model established pre-clinically, GSK3358699 is predicted to have a short systemic half-life of approximately 3 hours. However, the intracellular pharmacokinetics of GSK3206944 are less readily predicted. The study will therefore include intracellular quantification of GSK3206944 in all three parts.

To further investigate the potential use of GSK3358699 in immuno-inflammatory diseases, *in vivo* inflammatory challenges (blisters, LPS and GM-CSF) will be administered in both Part A (treatment Period 4 only) and Part C (Cohorts 4 and 8) of the study, should data support this. GSK3358699 modulates multiple pro-inflammatory pathways *in vitro* [GlaxoSmithKline Document Number 2017N333959_00], and therefore has potential utility across a broad range of diseases. With this in mind, cantharidin-induced blisters, LPS and GM-CSF challenges have been specifically selected as inflammatory challenges that are representative of the immune response encountered across a range of inflammatory conditions including fibrosis and RA. Inclusion of these challenges will illuminate which of these disease-relevant mechanisms GSK3358699 modulates most efficiently in an *in vivo* setting.

In Part A, these challenges will be administered at GSK3358699 C_{max}. In Part C the challenges may be administered at a time-point of low systemic GSK3358699 concentration, but high intracellular GSK3206944 concentrations. Taken together, this data may inform on systemic versus intracellular compound exposure as a key driver of PD response following pro-inflammatory *in vivo* challenges. A summary and rationale for the challenges to be used as part of this study is below:

• *Ex vivo* LPS challenge – GSK3358699 has shown concentration dependent inhibition of cytokine production in LPS stimulated blood *in vitro*. *Ex vivo* LPS challenge of blood from participants dosed with GSK3358699 is a minimally invasive high throughput method through which to investigate target engagement.

2017N332348_05

CONFIDENTIAL

- In vivo LPS challenge Human *in vivo* LPS challenges have been used as a methodology to induce systemic inflammation and produce many of the immunological (changes in leukocyte numbers and induction of inflammatory mediators and cellular activation markers) and physical signs of acute and chronic disease. The human LPS model of systemic inflammation has been applied to clinical pharmacology studies to assess therapeutic interventions for analgesics, asthma, effective adjuvants, sepsis, trauma, Type-2 diabetes, Alzheimer's disease and others [Fullerton et al 2016]. This study will investigate the effect of GSK3358699 on LPS-induced inflammation as measured by the phenotype of peripheral leukocytes and the production of inflammatory mediators and acute phase proteins over time.
- In vivo GM-CSF challenge GM-CSF has a broad range of activities across innate and adaptive immune cells and is recognised as a key mediator in a number of inflammatory diseases, such as arthritis, multiple sclerosis, colitis, pain and interstitial lung disease [Wicks et al 2016]. Leukine (Sargramostim) given intravenously results in a systemic GM-CSF challenge that mobilises neutrophils, eosinophils and monocytes from the bone marrow. A GM-CSF dose of 5 µg/kg (equivalent to intravenous infusion of 60 µg/m²), administered subcutaneously, is associated with a measurable leukocyte response but is well tolerated based on the literature [Gianni et al 1990, Lieschke et al 1989]. 1.5µg/kg dose infused intravenously over 2 hours provides the same exposure (AUC) due to the increased bioavailability and higher C_{max} concentrations (Cebon et al 1990). This study will investigate the effect of GSK3358699 on GM-CSF induced inflammation as measured by leukocyte numbers, soluble inflammatory mediators, as well as cellular activation markers on leukocytes, particularly monocytes, over a defined time course.
- Chemically induced skin blisters Cantharidin is a vesicant (an agent that causes blisters) and a strong inhibitor of protein phosphatases type 1 and 2A [Honkanen et al 1993], used clinically for the treatment of warts and molluscum contagiosum. Following contact with the skin, it is absorbed into the epidermis and activates proteases leading to intra-epidermal blistering [Bertaux et al 1988]. Blistering is limited to the suprabasal epidermis and lesions heal without scarring. Skin blister induction by cantharidin has been utilised in clinical pharmacology for more than 50 years as a model of acute inflammation, and provides methodology to investigate leukocyte trafficking, cellular activation states and detection of plethora of inflammatory mediators, including pro-fibrotic mediators, in the blister fluid. The combination of blisters with systemic inflammation (induced by LPS or GM-CSF) provides a unique methodology to detect the effects of systemic inflammation on local inflammation. This study will investigate the effect of GSK3358699 on cantharidin induced blisters in the presence of systemic inflammation, as measured by leukocyte numbers, cellular activation markers and soluble inflammatory mediators associated with autoimmune and fibrotic diseases.

This study will be conducted in healthy male participants for the following reasons:

- Patients with immuno-inflammatory diseases may have existing co-morbidities or be taking medications that may confound the interpretation of data for GSK3358699.
- It is yet to be determined whether patients would derive benefit from a short duration of dosing of GSK3358699; however, taking part in this study may stop them receiving other required treatments.
- Females are excluded from this study as the potential benefits do not outweigh the risks, particularly to women of child bearing potential and additionally, the use of challenge agents is not as well characterised in females.
- The pre-clinical testicular toxicology findings show that there is a sufficient safety margin to allow the inclusion of males, including males of reproductive potential, in this study.

This study includes a placebo component to allow for a valid evaluation of AEs attributable to treatment versus those independent of treatment and to serve as valid controls for the PD assessments.

5.5. Dose Justification

This study will assess the safety, tolerability, pharmacokinetics and pharmacodynamics of single (in the fed (Part B) and fasted state, Part A and B) and multiple (Part C) doses of GSK3358699 in healthy volunteers. Target engagement will be determined by the extent of MCP-1 inhibition following *ex vivo* LPS stimulation of participant blood. This PD end point will form a central parameter to be considered along with PK, safety and tolerability during dose escalation decisions. Additional endpoints such as TNF and IL-6 inhibition will also be considered.

5.5.1. Part A

The planned doses of GSK3358699 for Part A are shown in Table 2 and have been selected on the basis of the TE expected at the correspondent model predicted human PK exposures.

A dose of 1 mg resulting in a maximum MCP-1 target engagement below 10% has been selected as the starting dose. This dose is below the minimum anticipated biological effect level (MABEL) for GSK3358699, which is considered to be 3 mg QD, based on anticipated levels of target engagement at that dose. Human PK/PD predictions together with a description of PD assays are described further below. The 1 mg dose is below the maximal recommended starting dose based on Food and Drug Administration (FDA) Guidance for Industry Estimating Maximum Safe Starting Dose in Initial Clinical Trial for Therapeutics in Adult Healthy Volunteers [U.S. Department of Health and Human Services, Food and Drug Administration, Center for Drug Evaluation and Research (CDER), 2005]. Using the multiplication method, this includes a safety factor of greater than 200-fold based on the cynomolgus monkey NOAEL (10 mg/kg) which equates to a Human Equivalent Dose (HED) of 227 mg for a 70 kg human.

Planned dose	Max TE	C _{max}	AUC	Monkey Gen NOAEL f	der-averaged old cover	Rat Gende NOAEL f	
(mg)	(%)	(ng/ml)	(ng/ml h)	Cmax	AUC	Cmax	AUC
1	9	1	6	612	275	1473	316
3	32	3	17	205	92	493	105
10	72	9	57	61	28	148	32
20	87	19	113	31	14	74	16
35	94	32	199	18	8	42	9
45	95	42	255	14	6	33	7

Table 2Planned GSK3358699 doses

The current knowledge of pan-BET inhibitors suggests that a short duration, high level of target engagement is associated with a clinical reduction in inflammatory biomarkers.

Based on this, PK/PD modelling, where the PK was described by a compartment model and the PK/PD relationship by a maximum effect possible (E_{max}) model, suggests efficacy could be achieved at 35 to 45 mg QD, a dose giving 90% target engagement for 4 h.

The dose of GM-CSF to be administered to participants in treatment Period 4 of Part A will be $60 \ \mu g/m^2$. The dose of LPS to be administered to participants in treatment Period 4 of Part A will be 0.75 ng/kg. The dose of cantharidin will be a standard dose as detailed in Section 7.1, and used in the enabling study 207654 [GlaxoSmithKline Document Number 2016N309726_01]. This dose represents a substantial reduction in exposure compared to that recommended for therapeutic use; it is the dose that will be used for all blister induction in this study.

A solution formulation will be used for doses of < 10 mg GSK3358699, and a capsule formulation for higher doses. Currently, there is no indication as to the taste or palatability of GSK3358699 administered as a solution. For this reason, participants receiving GSK3358699 or placebo as a solution in water (in any part of this study) may also need to consume a flavoured sweet (for example a hard boiled sweet) prior to or immediately following dosing, provided this does not interfere with ongoing monitoring or study procedures. The need for ongoing taste masking will be determined by the DEC.

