7.1. Treatments Administered

2017N332348_05

Table 3Investigational Product and Placebo to match

Study Treatment name	GSK33	58699	Plac	cebo	
Formulation description	Solution of API in water for injection (0.2 mg/mL)	API filled capsule	Water for injection	Microcrystalline Cellulose filled capsule	
Dosage form	Oral solution	Capsules	Oral solution	Capsules	
Unit dose strength (Part A)	From 1 mg up to 10 mg*	From 10 mg to 70 mg**	N/A	N/A	
Unit dose strength (Part B)	To be confirmed (TBC) following Part A	TBC following Part A; minimum unit dose strength will be 3 mg*, maximum unit dose strength will be 70 mg**	N/A	N/A	
Unit dose strength (Part C)	TBC following Part A	TBC following Part A; minimum unit dose strength will be 3 mg*, maximum unit dose strength will be 70 mg**	N/A	N/A	
Route of administration	Oral	Oral	Oral	Oral	
Dosing Instructions	Required volume of 0.2 mg/mL aqueous solution to be swallowed. Following the solution administration a further 100mL of water will be added to the same vessel from which the treatment solution was administered and swallowed.	One capsule to be swallowed with 240mL of water.	Required volume of water to be swallowed Following the initial water administration a further 100mL of water will be added to the same vessel from which the treatment solution was administered and swallowed.	One capsule to be swallowed with 240mL of water.	
Physical	Clear colourless	Orange size 0	Clear colourless	Orange size 0	
description	solution	capsules	solution	capsules	
Packaging and Labelling	The study treatment and excipients will be provided in bulk in labelled bags within a labelled keg. The label will detail product description, lot number, expiry date, storage conditions and quantity.				
Manufacturer	GSK to provide bulk GSK3358699 active pharmaceutical ingredient (API), placebo excipient, capsule shells to clinical site. Clinical site to manufacture the products extemporaneously according to a manufacturing batch record.				

* It is planned that doses of 3 mg and above will be administered as a capsule formulation in Part B and Part C of the study, however the solution formulation dose strength range of 1 mg up to 10 mg will be retained for flexibility. ** Dose strengths up to 45 mg are planned for this study but higher doses may be required if predicted PK is not achieved with planned doses.

The formulation, method of preparation and dosing instructions will be same as for each part of the study.

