10.2. Sample Size Determination

10.2.1. Sample size assumptions

At each dose level studied in Part A there will be approximately nine participants; six randomised to each of the GSK3358699 treatment groups and three receiving placebo in any one period. In Part A, each participant will be randomised to one of three sequences for the dose escalation phase.

In Part B of the study there will be approximately six participants, all receiving GSK3358699 (randomised to either fed or fasted administration), each participant will be randomised to one of two sequences. In Part C approximately fourteen participants in Cohort 4 were planned (ten randomised to the GSK3358699 treatment group and four receiving placebo, in a 5:2 ratio). In Cohorts 5 - 7 approximately eighteen participants are planned (nine randomised to each of the GSK3358699 treatment groups and nine receiving placebo, in a 1:1 ratio) and in Cohort 8 approximately twenty subjects are planned (ten randomised to the GSK3358699 treatment group and ten receiving placebo, in a 1:1 ratio).

Refer to Section 7.2 for further information on sample size and randomisation changes in the event of any dose modifications.

The sample size is based on feasibility.

The primary objective of the study is safety, where the number of safety events would be of interest, for example the number of participants experiencing a particular adverse event. At each dose level in Part A six participants will receive GSK3358699. If 0/6 of a

particular safety event in the GSK3358699 group is observed, using a Bayesian approach to determine the credible interval around an observed safety event, we would assume a flat Beta (1,1) prior, and if we were to observe 1 safety event in 6 then the posterior distribution would be Beta (2, 6), where we can be 95% certain that the true probability of the safety event lies between 0.04 and 0.58.

Sample size sensitivity

A sample size sensitivity analysis has been conducted on the primary endpoint, to investigate different safety event rates. If the number of subjects who completed each active dose reduces, then the true incidence rates of safety events that could not be ruled out would change. These changes are outlined below:

N on GSK3358699 Completing Cohort	Number of a particular safety event observed with GSK3358699	Upper limit of exact 95%CI indicating that a true incidence rate of x% could not be ruled out
6	2	71%
6	3	82%
	0	46%
5	1	64%
	2	78%
	0	52%
4	1	72%
	2	85%

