5.2. Study Treatment Display Descriptors

In the Tables, Listings and Figures (TLF), treatment should be presented with placebo first, then in order of increasing dose within each part.

Part A	Part A: Treatment group descriptions				
Rand	andAll NG Data displays for reporting				
Code	RandAll description	Table/FigureListing LabelOrder in T		Order in TLF	
		Label			
А	1 mg GSK3358699 SD	1 mg SD	1 mg SD – A	2	
В	3 mg GSK3358699 SD	3 mg SD	3 mg SD – B	3	
С	10 mg GSK3358699 SD	10 mg SD	10 mg SD – C	4	
D	20 mg GSK3358699 SD	20 mg SD	20 mg SD – D	5	
Е	35 mg GSK3358699 SD	40 mg SD	40 mg SD – E	8	
F	45 mg GSK3358699 SD	30 mg SD	30 mg SD – F	7	
R	Dose X GSK3358699 SD	25 mg SD	25 mg SD – R	6	
P Placebo SD		Placebo SD	Placebo SD – P	1	
Note: doses in RandAll descriptions and display descriptions differ for treatments E, F, R					
due to DEC decisions.					

Part C: Treatment group descriptions					
RandAll NG		Data displays for reporting			
Code	Description	Table/Figure Label	Listing Label	Order in TLF	
Ι	Dose 1 GSK3358699 RD	10 mg RD	10 mg RD - I	2	
J	Dose 2 GSK3358699 RD	10 mg RD	10 mg RD - I	2	
QPlacebo RDPlacebo RD - Q			1		
Note: the same dose level was administered in both Cohorts 4 and 5 due to the early					

Note: the same dose level was administered in both Cohorts 4 and 5 due to the early termination of Cohort 4. Subjects in the active treatment group from both cohorts will be summarised and listed under the same treatment label.

207546

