9.1.5. Statistical Analyses / Methods

Details of the planned displays are presented in Appendix 9: List of Data Displays and will be based on GSK Data Standards and statistical principles.

Unless otherwise specified, endpoints / variables defined in Section 9.1 will be summarised using descriptive statistics, graphically presented (where appropriate) and listed.

9.1.5.1. **Dose proportionality (Part A)**

Dose proportionality will be assessed for GSK3358699 by visual inspection of:

- Part A (single dose - fasted state): dose normalised AUC(0-∞) [or if not available AUC(0-t)] and Cmax values versus dose.

If data permits, dose proportionality may also be assessed for GSK3358699 using the power model described below.

Dose proportionality (Parts A and C)			
Endpoints			
• Part A (single dose - fasted state): AUC(0-t), AUC(0-∞) and Cmax			
Model specification			
• Power model (log-log linear model):			
$y = \alpha \times dose^{\beta} \iff \log_e(y) = \log_e(\alpha) + \beta \times \log_e(dose)$			
Where			
\circ y = endpoint of interest			
\circ dose = actual dose received under fasted condition			
$\circ \beta$ = parameter associated to dose (slope)			
$\circ \alpha$ = participant-specific random effect (intercept)			
• Terms fitted in the power model:			
• Response: log transformation of the endpoint of interest $\log_e(y)$			

207546

- Fixed continuous covariates: $\log_e(dose)$
- Random: participant
- The Kenward and Roger method for approximating the denominator degrees of freedom and correcting for bias in the estimated variance-covariance of the fixed effects will be used.
- An unstructured covariance structure on the random effects terms (SAS: G matrix, random statement) will be used.

Model checking & diagnostics

- Normality assumptions underlying the model used for analysis will be examined by obtaining a normal probability plot of the residuals and a plot of the residuals versus the fitted values (i.e. checking the normality assumption and constant variance assumption of the model, respectively) to gain confidence that the model assumptions are reasonable.
- If there are any departures from the distributional assumptions, alternative models will be explored using appropriate transformed data.

Model results presentation

Table of the estimated slopes and 90% CI (slope close to 1 implies dose proportionality). The following will be derived:

- Fold-increase for doubling dose: 2^{β} , where β is the slope

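### In Part A formulation changes with dose, and neither the SAP's dose-proportionality slope nor its dose-normalised plots separate the two

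*Protocol*

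**What the plan says.** **Formulation.** Protocol Section 5.5.1 gives the rule for Part A: "A solution formulation will be used for doses of < 10 mg GSK3358699, and a capsule formulation for higher doses". In Protocol Table 3 (Section 7.1) the Part A solution strengths run "From 1 mg up to 10 mg" and the Part A capsule strengths "From 10 mg to 70 mg". Exactly 10 mg is thus unassigned by the sentence and lies in both ranges of the table. The table footnote limits the low-strength capsule to the later parts: "It is planned that doses of 3 mg and above will be administered as a capsule formulation in Part B and Part C". It does not alter the split at 1 and 3 mg in Part A.

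**Doses.** SAP Section 5.2 warns: "Note: doses in RandAll descriptions and display descriptions differ for treatments E, F, R". The doses reported for Periods 1-3 are 1, 10 and 40 mg in Cohort 1 and 3, 20 and 30 mg in Cohort 2, with 25 mg in Period 4. Protocol Section 10.2.1 adds: "At each dose level in Part A six participants will receive GSK3358699".

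**Analysis.** SAP 9.1.5.1 begins with visual inspection of dose-normalised AUC and Cmax against dose. If the data allow, it then adds a power model with participant as a random effect and log dose as the only fixed covariate, where "dose = actual dose received under fasted condition". The result is read by the rule "slope close to 1 implies dose proportionality", with a 90% CI and the fold-increase per doubling. Table 3.5 in SAP 13.9.7 is a planned output, split by endpoint only. Neither document mentions a formulation term, a capsule-only fit or a caveat.

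**The concern.** All the low doses are in one dosage form and all the high doses in the other, and no dose is planned in both. If the capsule delivers more or less drug than the solution, exposure steps up or down somewhere between 3 and 20 mg. With log dose as the only fixed effect, that step can go only into the slope or the residual. The dose-normalised plot shows the same step, and a reader cannot tell formulation from dose if the points are not marked.

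The bias has no fixed direction. Lower capsule exposure makes a proportional drug look less than proportional, or hides a true slope above 1. Higher capsule exposure does the reverse.

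A second, smaller matter is Period 4. It is single-dose, fasted (Protocol 6.3.1) and PK-sampled (Protocol 2.1.1), so as worded it enters the model. LPS or GM-CSF is given around Cmax in that period.

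**Working it through.** The documents give no precision target or operating characteristic for this slope, so there is no figure of theirs to reproduce. As context, the predicted exposures in Protocol Table 2 regress on dose (log-log) with slope 0.988 for AUC and 0.977 for Cmax. The planning predictions were therefore close to proportional.

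**Inputs from the documents.** Periods 1-3 have 18 participants with two active doses each, three per sequence. The dose pairs are (10, 40), (1, 40), (1, 10), (20, 30), (3, 30) and (3, 20) mg. That gives 36 active profiles, six per dose.

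**Assumptions.** F is the capsule/solution exposure ratio. Between/within-participant log-SDs are 0.20/0.15, 0.30/0.25 and 0.40/0.30.

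**Step 1: share of the formulation step that enters the slope.** If log(y) = a_i + b·log(dose) + ln(F)·[capsule], the fitted slope has bias g·ln(F). Here g is the coefficient of the capsule indicator regressed on log dose under the same model.

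Hand check with equal weights and 10 mg as capsule:
- The six log doses are 0, 1.099, 2.303, 2.996, 3.401 and 3.689, with mean 2.248.
- Their squared deviations sum to 10.34.
- The deviations of the four capsule doses sum to 3.397.
- So g = 3.397 / 10.34 = 0.33.

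Generalised least squares with the random participant effect gives g = 0.337. If 10 mg was solution, g is about 0.31. Adding Period 4 at 25 mg leaves it at about 0.34.

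**Step 2: slope shift when the true slope is 1.**

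| F | ln(F) | 0.337·ln(F) | fitted slope | fold per doubling |
|---|---|---|---|---|
| 0.9 | -0.105 | -0.035 | 0.965 | 1.95 |
| 0.8 | -0.223 | -0.075 | 0.925 | 1.90 |
| 0.7 | -0.357 | -0.120 | 0.880 | 1.84 |
| 1.25 | +0.223 | +0.075 | 1.075 | 2.11 |

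Masking works the same way: a true slope of 1.075 with F = 0.8 would give 1.075 - 0.075 = 1.00.

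**Step 3: precision.** Half-width = 1.74 × SE (t on 17 df), with 10 mg as capsule.

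| log-SD between/within | all doses: SE, half-width | capsule only (10-40 mg): SE, half-width |
|---|---|---|
| 0.20/0.15 | 0.0215, 0.037 | 0.072, 0.125 |
| 0.30/0.25 | 0.036, 0.062 | 0.118, 0.205 |
| 0.40/0.30 | 0.043, 0.075 | 0.144, 0.25 |

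The 0.035 shift at F = 0.9 is inside the half-width throughout. The 0.075 shift at F = 0.8 exceeds it in the first two rows and equals it in the third. At a within-participant SD of 0.40 the half-width is 0.098, and the 0.075 shift is inside it.

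**Step 4: the alternatives.** The capsule-only fit keeps 24 of 36 profiles. Only six participants contribute two capsule doses, and the range falls from 40-fold to 4-fold. A formulation fixed effect on all doses, at CVs of 25% within and 30% between, has SE 0.093 and half-width 1.74 × 0.093 = 0.16. Because no dose is planned in both forms, that term is separable from curvature only by assuming log-linearity.

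If 10 mg was solution, the capsule-only fit at the same CVs has SE 0.29 (half-width 1.74 × 0.29 = 0.50), against SE 0.066 (1.74 × 0.066 = 0.11) with a formulation term.

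**The case against.** The case for leaving the plan alone has real weight.

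- **The power model is optional and comes second.** A step near 10 mg could be noticed by eye. That holds only if the plot shows which points are solution, and Table 3.5 is planned regardless. The SAP's residual checks lead to other models when distributional assumptions fail; a step largely absorbed by the slope need not trigger them.
- **There is no test.** A reader might infer a false-positive rate. At F = 0.8 the 90% CI would exclude 1 in about 96%, 65% and 51% of trials over the three SD settings, against a nominal 10%. The documents do not support that reading. Protocol 10.1 and SAP 2.4 disclaim formal hypotheses, the SAP has no CI-exclusion rule, and a fold-increase of 1.90 per doubling might fairly be called close to proportional.
- **The ratio is unknown.** Nothing in the documents shows that the formulations differ. If they are equivalent there is no bias.
- **Capsule-only estimation often does worse.** At SDs 0.30/0.25, root mean squared error (all-dose against capsule-only) is 0.050 against 0.118 at F = 0.9, 0.083 against 0.118 at 0.8, and 0.125 against 0.118 at 0.7. This rules out making the capsule-only slope the basis of the conclusion.
- **No dosing decision rests on the slope.** Escalation is governed by exposure limits and PK predictions (Protocol 8.1.7). This is descriptive secondary PK in a study that ended early.
- **Period 4.** It is tempting to say the challenge distorts exposure. The documents do not say that LPS or GM-CSF changes GSK3358699 PK, and including 25 mg barely moves g.

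These points limit the consequence. They do not remove the confounding or justify leaving it undisclosed.

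**Conclusion.** The confounding is in the documents and holds whichever form was used at 10 mg. About one third of any log exposure difference between formulations enters the pooled slope. The effect is small for a 10% difference. For a 20% difference it is as large as the 90% half-width or larger, provided the within-participant log-SD is 0.30 or less. The formulation ratio and the SDs are assumptions, so the size is conditional. The documents support neither a claim that the formulations differ nor a claim that the SAP would reach a wrong conclusion at a known rate. They do show a slope and plots that cannot be read as pure dose effects and carry no warning of it. This is an inexpensive improvement to a secondary analysis; it does not invalidate the plan.

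**What to change.** In SAP 9.1.5.1:

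1. Keep the all-dose slope, fitted to Periods 1-3.
2. Report beside it, as a sensitivity analysis, either a slope from the capsule doses only or one from all doses with a formulation fixed effect. Classify 10 mg by the form actually given and list formulation by dose. If 10 mg proves to have been solution, the formulation-term version is much the more precise of the two.
3. Mark formulation by symbol in the dose-normalised plots.
4. Show the 25 mg Period 4 challenge data separately.
5. State proportionality across the full range only if the two slopes agree, or with a formulation caveat. Given the width of the second interval, agreement is weak reassurance and should be worded so.

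The cost is SAP wording and one extra model run, with no new data. The drawback is the imprecision of the capsule-only slope (90% half-width about 0.13 to 0.25 with 10 mg as capsule), which is why it supplements the pooled slope and does not replace it.
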